3.2 Secondary Objectives

To evaluate physical parameters and patient reported symptoms and satisfaction with treatment after 52 weeks of dupilumab using validated dermatologic and non-dermatologic instruments.

4 STUDY DESIGN

4.1 Study Overview

This is a single-center study. Up to thirty subjects with moderate to severe atopic dermatitis will receive dupilumab for a treatment period of 52 weeks. Patients will be evaluated using validated dermatologic and non-dermatologic psychometric instruments throughout the study period to measure quality of life, as well as satisfaction and symptom measures. Additionally, patients will

record their experience with the study drug at home during the study period. See Appendix 1 for a timeline of study activities.

5 CRITERIA FOR EVALUATION

5.1 Primary Analysis Endpoint

Improvement in quality of life measured by change in Psychological General Well-Being scale (PGWB) at Week 16 from baseline.

5.2 Secondary Analysis Endpoints

1. Improvement in work productivity measured by change in Work Productivity and Activity Impairment scale (WPAI) at Week 16 from baseline
2. Improvement in quality of life measured by change in Dermatology Life Quality Index (DLQI) at Week 16 from baseline
3. Efficacy of drug as measured by EASI and IGA at week 16 from baseline
4. Safety of drug
5. Improvement in itch and pain scores using numerical rating scales at Week 16 from baseline
6. Improvement in sleep quality measured by the Pittsburgh Sleep Quality Assessment (PSQI) at Week 16 from baseline
7. Evaluation of subjective video documentation

5.3 Safety Evaluations

Safety and tolerability to dupilumab will be assessed by adverse events, vital signs, physical examinations (including skin examinations and injection-site evaluations), and concomitant medication review. Laboratory assessments will be performed at screening.

6 SUBJECT SELECTION

6.1 Study Population

Subjects will be selected from qualified volunteers at least 18 years of age, with stable (unchanged for 2 months), moderate to severe atopic dermatitis who are candidates for phototherapy or systemic therapy.

6.2 Inclusion Criteria

1. Ability to provide written informed consent and comply with the protocol
2. At least 18 years of age
3. Diagnosis of atopic dermatitis at least 6 months prior to enrollment, having stable (unchanged) disease for at least 2 months

4. Non-immune-compromised status
5. Subjects have moderate-to-severe atopic dermatitis, classified as Eczema Area and Severity Index (EASI) score greater than or equal to 6
6. Subject is considered a candidate for phototherapy or systemic therapy
7. Subjects of child-bearing potential must have a negative urine pregnancy test within 7 days prior to first dose of dupilumab
8. Sexually active subjects of childbearing potential must agree to use medically acceptable form of contraception during screening and throughout the study
9. Subject meets concomitant medication requirements as documented below

6.3 Exclusion Criteria

1. Younger than 18 years of age
2. Has mild atopic dermatitis, classified as EASI score less than 6
3. History of known or suspected intolerance to any of the ingredients of the investigational study product
4. Evidence of skin conditions other than atopic dermatitis that would interfere with study-related evaluations of atopic dermatitis
5. History of immune-compromised status [e.g. human immunodeficiency virus (HIV) positive status or other immune suppressing drug] or a congenital or acquired immunodeficiency
6. Has a poorly controlled medical condition including, but not limited to, unstable cardiovascular disease, poorly controlled diabetes, recent stroke, history of recurrent infections, or any other condition for which, in the opinion of the investigator, participation in the study would place the subject at risk
7. Has a history of or ongoing drug or alcohol abuse
8. Is not willing to comply with concomitant medication requirements
9. Is known, or suspected of being unable to comply with the study protocol
10. Subjects who are well controlled on current treatment for atopic dermatitis and participation in the study may worsen disease control significantly
11. Subjects who have been previously treated and/or are currently on dupilumab will not be eligible to participate.

7 CONCURRENT MEDICATIONS

7.1 Allowed Medications and Treatments

As this is a real-world trial, during the course of the study, subjects may continue treatment with topical steroids, phototherapy, or other systemic agents as deemed appropriate by the study investigators.

Any medications that the subject receives during the study must be recorded. Vaccines administered to the subject should be listed as a concomitant medication.

7.2 Prohibited Medications and Treatments

During the study period, concurrent use of other biologic medications apart from the study medication is prohibited. No new treatments should be added during the study period that the patient was not using consistently prior to study onset.

8 STUDY TREATMENTS

8.1 Supply of Study Drug at the Site

Regeneron will ship the study drug to the investigational sites. The study drug is supplied in cartons containing either two 300 mg/2 mL solution pre-filled syringes with needle shield or 2 pre-filled syringes. Each kit of study drug will be labeled with the required FDA warning statement, the protocol number, and directions for use and storage.

8.2 Storage

Dupilumab must be refrigerated at 36°F to 46°F (2°C to 8°C) in the original carton to protect from light. The medication will be kept in a temperature-monitored refrigerator at the study site. If necessary, pre-filled syringes may be kept at room temperature up to 77°F (25°C) for a maximum of 14 days. The product will be kept in the original carton until the time of use.

8.3 Dosage/Dosage Regimen

Dupilumab will be administered at an initial dose of 600 mg subcutaneously followed by 300 mg subcutaneously through the study, which is the FDA-approved and recommended dose for dupilumab. There is no weight-based dosing. The dosing schedule will be as follows: dupilumab 600mg subcutaneously once at week 0, followed by dupilumab 300 mg subcutaneously every other week until week 50.

8.4 Administration Instructions

Doses of study treatment will be administered at the study site after the study assessments for the visit have been completed, at visits occurring between weeks 0 and 48. Subjects will administer the medication independently every other week only after they have demonstrated the competency to self-administer the treatment outside of the study site. Patients not demonstrating competency to self-administer the treatment will be administered the medication at the study site as needed. There will be no study medication given after week 50 of the study.

The subject should be instructed to contact the investigator if he/she is unable for any reason to attend a study visit as scheduled. All dates and times of injections done to the subject during the study must be recorded on the Dosage Administration Record CRF. The investigator will promote compliance by instructing the subject to attend the study visits as scheduled and by stating that compliance is necessary for the subject's safety and the validity of the study.

8.5 Study Drug Accountability

The qualified site personnel will maintain an accurate record of the shipment and dispensing of study treatment in a treatment accountability log. All study treatment kits assigned to the subject during the study will be recorded.

8.6 Measures of Treatment Compliance

Subjects will be given scheduled doses of dupilumab at each visit from visit 2 (week 0) until visit 14 (week 48). Subjects will be given a dosing diary at every visit between weeks 0 and 48 to record their scheduled injections administered at home every other week.

9 STUDY PROCEDURES AND GUIDELINES

A Schedule of Events representing the required testing procedures to be performed for the duration of the study is diagrammed in Appendix 1.

Prior to conducting any study-related activities, written informed consent and the Health Insurance Portability and Accountability Act (HIPAA) authorization must be signed and dated by the subject.

All clinical assessments will take place at the study site at [name].

All blood draws will take place at UCSF Blood Draw Lab at Mount Zion at [name].

9.1 Clinical Assessments

9.1.01 Medical History

Relevant medical history, including history of current disease and previous atopic dermatitis treatment, and information regarding underlying diseases will be recorded at Screening.

9.1.02 Concomitant Medications

All concomitant medication and concurrent therapies will be documented at Screening, at every site visit, and at early termination when applicable. Dose, route, unit frequency of administration, indication for administration, and dates of medication will be captured.

9.1.03 Demographics

Demographic information (date of birth, age, gender, ethnicity) will be recorded at Screening.

9.1.04 Physical Examination

A complete physical examination will be performed by either the investigator or a sub-investigator who is a physician at Screening. New abnormal physical exam findings must be documented and will be followed by a physician or other qualified staff at the next scheduled visit.

9.1.05 Vital Signs

Body temperature, blood pressure, pulse, and respirations will be performed after resting for 5 minutes at all site visits. Height and weight will additionally be measured at each study visit.

9.1.06 Adverse Events

Information regarding occurrence of adverse events will be captured at weeks 4, 8, 12, 16, 20, 24, 28, 32, 36, 40, 44, 48, 52, and at early termination when applicable. Duration (start and stop dates and times), severity/grade, outcome, treatment and relation to study drug will be recorded on the case report form (CRF).

9.1.07 EASI and IGA

Eczema Area and Severity Index (EASI) and Investigator Global Assessment (IGA) will be completed at Screening and weeks 0, 4, 8, 12, 16, 20, 24, 28, 32, 36, 40, 44, 48, 52, and at early termination when applicable.

9.1.08 Quality of life measures

Quality of life measures will be assessed at weeks 0, 4, 8, 12, 16, 20, 24, 28, 32, 36, 40, 44, 48, 52, and at early termination when applicable.

Quality of life measures will be assessed using the following validated instruments:

- 1) Psychological General Well-Being scale (PGWB)
- 2) Work Productivity and Activity Impairment scale (WPAI)
- 3) Dermatology Life Quality Index (DLQI)

9.1.09 Symptom and satisfaction measures

Symptom and satisfaction measures will be assessed at weeks 0, 4, 8, 12, 16, 20, 24, 28, 32, 36, 40, 44, 48, 52, and at early termination when applicable.

Symptom and satisfaction measures will be assessed using the following validated instruments:

- 1) Itch Numerical Rating Scale
- 2) Pain Numerical Rating Scale
- 3) Pittsburgh Sleep Quality Assessment (PSQI)

9.1.10 Photography

Photographs (full front and back, excluding the face) will be taken at weeks 0, 16, 24, 52, and at early termination when applicable.

9.1.11 Video recording

Patients will be given a video recording device at week 0, and will be instructed on how to use it to record video. Patients will be instructed to record videos of themselves at home discussing their experience with the study drug and its impact on their skin and quality of life for roughly 5-10 minutes/week. The patient will be the only person in the video (i.e. there will be no family members or others interviewing or participating in the video). The patient will be encouraged to

record in a private setting (i.e. alone in their bedroom or office) and similarly, will be instructed to keep the recording device and its stored footage in a private location. Patients will be given a list of topics at the week 0 visit to be used as guidelines for discussion:

- 1) Please discuss any changes you have observed in your skin while using the study drug.
- 2) What is the most important change that you have experienced while using the study drug?
- 3) What are your goals with undergoing this medication for the future?
- 4) Please discuss how these changes in your skin have impacted both your life (day-to-day behaviors such as clothing choice or activities) and the lives of your loved ones.
- 5) Please discuss any changes in how you feel since starting the study medication (mood, sleep, work, home life, personal relationships).
- 6) Please discuss your overall experience using the study drug.
- 7) Please discuss any interesting or notable experiences or events that have occurred to you while using the study drug.
- 8) Please feel free to discuss anything else pertaining to your experience with eczema

Patients will be instructed to bring in their video recording devices to their study visits at weeks 4, 8, 12, 16, 20, 24, 28, 32, 36, 40, 44, 48, 52, and at early termination when applicable. At these visits, study staff will download the patient videos to a secure local storage site.

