Beyond administering these questionnaires, we will also take a novel approach to assessing patient experience with a medication. Each patient will be given a video recording device to document their experience from a pre-dupilumab state to a post-dupilumab state in the privacy of their own home. Human-interest stories excite payers and the general public who are not healthcare providers. It is best to have both human-interest stories in a narrative form before and after treatment as well as quantitative documentation with the PGWB and WPAI.

It is hoped that the information gained from this study will not only provide more insight into the psychosocial and occupational impact of AD, but also confirm the value of dermatological care by demonstrating and documenting how an effective treatment modality like dupilumab can reverse these negative impacts.

Thus, in this real-world study of atopic dermatitis, we aim to examine the value and efficacy of medical intervention, extending beyond physical improvement, and into the realm of psychosocial and occupational functions.

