14.2 Analysis of Secondary Endpoints

1. Efficacy Endpoints

- a.** EASI and IGA scores at week 16 will be compared to baseline.

2. Safety Endpoints

- a.** Safety will be evaluated by tabulation of adverse events (AEs), including any Serious Adverse Events (SAEs) within treatment groups. All AEs occurring during the study will be recorded. Descriptions of adverse events will include the date of onset, the date the adverse event ended, the severity of the adverse event, and the outcome. All reported adverse events will be summarized by the number of subjects reporting adverse events, body system, severity, seriousness, and relationship to study treatment.

3. Analysis of Other Endpoints

- a.** Other variables may be analyzed and presented descriptively. The methods to be used will include (but are not limited to) parametric and nonparametric analysis, means, standard deviations, frequency counts and graphs, as appropriate.
- b.** Video footage of patient experiences will be compiled at the end of the study. The compiled video footage will subsequently be watched and analyzed to further understand the experiences of atopic dermatitis patients, and how undergoing dupilumab treatment alters these patients' experiences and attitudes with their skin disease.

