14.3 Sample Size

Up to 30 subjects will receive dupilumab for a treatment period of 52 weeks (i.e. last injection on week 50). This is based on previous similar studies investigating the impact of adalimumab and ustekinumab on QoL in psoriasis patients which included 33 and 36 patients, respectively.

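### The video topics for secondary endpoint 7 lean towards change: two of eight presuppose it, and none names no change, worsening or unwanted effects

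*Combined protocol and SAP*

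**What the plan says.** Section 5.2 lists "Evaluation of subjective video documentation" as the seventh secondary endpoint, with no time point and no measure.

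Section 9.1.11 describes the collection. "Patients will be given a video recording device at week 0, and will be instructed on how to use it to record video". At home they speak to the camera, "discussing their experience with the study drug and its impact on their skin and quality of life for roughly 5-10 minutes/week". Nobody else may appear or ask questions. One list of eight topics, given out at the Week 0 visit, guides what they talk about. Topic 2 reads "What is the most important change that you have experienced while using the study drug". The recordings are gathered throughout follow-up: "Patients will be instructed to bring in their video recording devices to their study visits at weeks 4, 8, 12, 16, 20, 24, 28, 32", and so on to Week 52 or early termination.

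Section 14.2 places the analysis under other endpoints. The footage is compiled when the study ends, and then: "The compiled video footage will subsequently be watched and analyzed to further understand the experiences of atopic dermatitis patients". The same sentence adds the aim of seeing how treatment alters those experiences and attitudes. Section 2 gives a further purpose: "Human-interest stories excite payers and the general public who are not healthcare providers". Section 14 promises a detailed SAP before the final data are analysed.

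**The concern.** With no interviewer present, the topic list is the main influence on what patients choose to say. Nobody can ask the follow-up question that would bring out a flat or unfavourable course. If the list takes change for granted and never mentions its absence or its opposite, a patient with little to report is nudged to find something. A patient who is worse, or troubled by side effects, must raise that unprompted.

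At stake is how far endpoint 7 can be believed. Section 14.2 wants to learn from the videos how treatment alters patients' experience, and Section 2 intends the narratives for payers and the public. A favourable set of videos would carry more weight if the questions had invited unfavourable answers equally.

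**Working it through.** No test, threshold or effect size attaches to this endpoint, so the main check is a reading of the eight topics in Section 9.1.11.

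| Topic | Subject matter (paraphrased) | Reading |
|---|---|---|
| 1 | Any skin changes noticed on the drug | Framed around change; allows none |
| 2 | The change that mattered most | Presupposes a change; no direction given |
| 3 | Future goals with the medication | Not about observed change |
| 4 | How the skin changes affected the patient's life and family | Presupposes a change; no direction given |
| 5 | Any changes in mood, sleep, work, home life, relationships | Framed around change; allows none |
| 6 | Overall experience of the drug | Open |
| 7 | Notable experiences or events | Open |
| 8 | Anything else about the eczema | Open |

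Counts: 2 presuppose change (topics 2 and 4), 2 are framed around it (1 and 5), 1 concerns goals (3) and 3 are open (6, 7, 8); 2 + 2 + 1 + 3 = 8. Topics that name no change, worsening or unwanted effects: 0 of 8.

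Two features of the design add to the influence of the wording. Section 9.1.11 provides one list for the whole year, with no interviewer. Section 10.02 hands out the recorder at the visit of the first injection, so no home recording before the first dose is scheduled. What the videos say about change therefore rests on the patient's own account under these topics.

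For scale, the documents state no total for the footage. Inputs: at most 30 subjects (Section 14.3), 52 weeks, and 5 to 10 minutes a week (Section 9.1.11).

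- Hours = subjects × weeks × minutes per week / 60
- Lower: 30 × 52 × 5 / 60 = 130 hours
- Upper: 30 × 52 × 10 / 60 = 260 hours
- Per subject: 52 × 5 / 60 = 4.3 hours to 52 × 10 / 60 = 8.7 hours

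This is a ceiling, since it takes full enrolment, a recording every week and no dropout. With an assumed 20 subjects it is 20 × 52 × 5 / 60 = 87 to 20 × 52 × 10 / 60 = 173 hours. The figures bear only on the side note about the SAP. They say nothing about the direction or size of any bias.

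**The case against.** The strongest defence is that the list is not one-sided. Topics 2 and 4 do not say that the change is good, and the most important change could be a worsening. Topics 1 and 5 can be answered with none. Topics 6 to 8 leave room for side effects and disappointment, and the whole list is offered only as guidance. All of this is correct. It is why the point is an opening for bias and not a demonstrated one.

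A reader might infer that the video result *is* tilted towards benefit, especially given the purpose stated in Section 2. The documents do not support that. They contain no results and no means of sizing the effect of the wording. Section 2 also calls the videos a new way to assess patient experience, to stand beside the quantitative PGWB and WPAI data.

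A reader might also infer that favourable footage will be picked out once outcomes are known. The documents do not support that either. Compiling the footage in Section 14.2 can mean gathering all of it, and up to 260 hours, though heavy, is 260 / 40 = 6.5 forty-hour weeks for one viewer. The SAP promised in Section 14 can still set the method.

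Little else depends on the videos. The primary PGWB comparison and the EASI and IGA comparisons are independent of them, and Section 11.1 seeks adverse events by non-directive questions at each visit. That protects the safety data, though it does nothing for endpoint 7. It does show that the protocol already uses neutral questioning elsewhere.

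The SAP does not answer the point about wording. It can decide how footage is sampled and coded, but it cannot obtain answers to questions that were never put during a year of recordings.

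**Conclusion.** The point holds as a modest one. Two of the eight topics presuppose change, two more are framed around it, and none names no change, worsening or unwanted effects. Endpoint 7 is therefore open to bias towards reporting change or benefit. Whether bias would occur, and how large it would be, cannot be determined from the documents.

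The conclusion assumes that patients broadly follow the list they are given, which is likely when they record alone but is not guaranteed. It is confined to one descriptive secondary endpoint. The improvement is worth making because it is cheap and is available only for recordings not yet made.

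**What to change.** In Section 9.1.11, reword topics 1, 2, 4 and 5 so that each direction is offered equally, for example: *describe your skin, mood, sleep, work and daily life this week, whether better, the same or worse*. Add one topic that asks about unwanted effects or disappointments. Topics 3 and 6 to 8 can stay.

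The cost is a revised topic list and an IRB submission. Any subjects already enrolled will have recorded under the current list, so the report should say which list each recording followed. Sample size, visits and the primary analysis are unaffected.

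As a secondary note, the SAP promised in Section 14 should state, before any footage is viewed, whether all of it or a pre-set sample is analysed, and by what method.

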9.1 Clinical Laboratory Measurements

9.2.01 Hematology

Blood will be obtained and sent to the clinical hematology lab for a complete blood count (hemoglobin, hematocrit, red blood cell count, white blood cell count, white blood cell differential, and platelet count) for determination of systemic evidence for infection and/or inflammation at Screening.

9.2.02 Blood Chemistry Profile

Blood will be obtained and sent to the clinical chemistry lab for determination of electrolyte levels, serum BUN, creatinine, AST, ALT, and alkaline phosphatase at Screening.

